6.4 Details of Laboratory Studies

Testing

Swabs for MRSA:	Patients will have their nares, throat, groin, axilla, and perirectal areas swabbed for MRSA colonization and these swabs will be sent to the microbiology laboratory at the clinical site for determination of the presence of MRSA or MSSA at each of these sites. The laboratory will provide culture results within 3-4 days of swab collection.
Wound and blood cultures:	Patients with an active skin or soft tissue infection will have a culture of the wound performed and sent to the microbiology laboratory of the clinical site for determination of the presence of MRSA or MSSA at each of these sites. Blood cultures may be ordered based on the discretion of the primary physician.
HIV studies:	CD4 count by flow cytometry and HIV viral load will be performed at each clinical site's lab.
Pregnancy test:	Women of childbearing age will have a pregnancy test at baseline to assure she meets inclusion/exclusion criteria. This test will be repeated if she is found to be colonized with MRSA before dispensing the decolonization medications; if she is found to have a positive pregnancy test, her study participation will be terminated.

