6.10 Termination

A subject's participation will be terminated if one of the following occurs:

- a. Subject voluntarily withdraws
- b. Subject fails to comply with study procedures
- c. Decision in the best interest of the patient
- d. Patient is no longer eligible for care at the military HIV clinics
- e. Patient becomes pregnant or decides to become pregnant during the two-year study period

- f. The patient begins employment as a healthcare worker with direct patient contact

A subject who develops a rash or significant adverse event due to study medication will be discontinued from treatment but will be encouraged to continue to undergo follow up including study visits for completing questionnaires and swabs for MRSA colonization every 6 months (+/- 2 months) until study completion; the patient will not be randomized to one of the treatment arms if he/she is found to be positive again for MRSA colonization. The subject may be withdrawn from the study if it is felt by the clinical investigators that the subject is at an undue risk from further participation.

The subject will require a termination visit if withdrawn from the study. If a subject's participation in this study is terminated, they will be offered medical standard of care and a medical evaluation, to include clinical laboratory studies as needed. The investigator will complete the Completion/Discontinuation CRF.

VII. STATISTICAL ANALYSES

There are four primary questions to be answered to address this study's primary objective. These, and an analysis designed to answer the question, follow.

- (1) What is the hexachlorophene/mupirocin treatment effect to clear MRSA colonization compared to placebo? We will also examine if these decolonization procedures are effective at reducing MRSA infections and skin/soft tissue infections compared to placebo. We propose to pool the data at 6, 12, 18, and 24 months as if they were independent and conduct a chi-square or Fisher's exact test of contingency. These analyses will be conducted for colonization and infection separately. The proposed pooling of this study design assumes that there is no persistent or repeated-treatment effect and that there is no patient-to-patient difference in susceptibility. These effects will be investigated in the following questions.

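### Section 6.10 ends follow-up as well as study product for non-compliance, pregnancy and new patient-facing healthcare work, so a patient terminated between randomization and the next 6-month visit loses the primary outcome swab

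*Combined protocol and SAP*

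**What the plan says.** Section 6.10 opens its list by stating that a subject's "participation will be terminated if one of the following occurs". The list has six items. Three matter here:

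- item b: "Subject fails to comply with study procedures", with no definition or threshold;
- item e: "Patient becomes pregnant or decides to become pregnant during the two-year study period";
- item f: "The patient begins employment as a healthcare worker with direct patient contact".

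The list makes no exception for patients already randomized. The next paragraph treats a rash or significant adverse event from study medication differently. Such a patient "will be discontinued from treatment but will be encouraged to continue to undergo follow up including study visits" and is not randomized again. Section 6.10 then adds: "The subject will require a termination visit if withdrawn from the study". It does not say which assessments that visit includes.

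The pregnancy rule recurs elsewhere. Section 6.4 says of the pre-dispensing test that "if she is found to have a positive pregnancy test, her study participation will be terminated". Sections 6.3 and 6.7 and the Appendix D footnote say the same in substance, and section 18.C.6 excludes women who become or plan to become pregnant.

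Section VII makes the 6-month visit after the initial randomization part of the primary endpoint and asks for at least 50 subjects with those data. It names no as-randomized analysis set and no rule for a missing 6-month swab. Its only allowance for loss is 50 drop-outs among 550 enrolled.

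**The concern.** The protocol meets one need, stopping product while keeping the outcome, in two ways. After a drug reaction the outcome is still collected. Under items b, e and f it is not.

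Item b matters most. Whether a patient complies may depend on the arm and on whether carriage persists. If the removed patients are more often still colonized and come mainly from the active arm, the patients left in the comparison make decolonization look better than it was in everyone randomized to it. Items e and f have no evident link to arm or outcome. Their cost is mainly outcome data lost for no statistical reason, in a trial that expects few randomized patients.

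**Working it through.** **1. Where the outcome can be lost.** Set side by side, the sections give this sequence:

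- Randomization follows a positive swab (6.7), and the endpoint needs the next 6-month visit (VII).
- Local patients have swabs every 28 days in between. Non-local patients have none until the 6-month visit (6.3).
- Termination in that interval ends both. Termination after the 6-month swab loses nothing for that randomization.
- The termination visit does not clearly fill the gap. The assessment list in 6.3 includes the five swabs at unscheduled visits, but Appendix D has no termination column and marks no swabs under its additional or unscheduled visit. Even if swabs are taken, they need not fall at 6 months.

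**2. The plan's own sample size reproduces.** Inputs from section VII: 85% versus 39% still colonized, power 0.80, alpha 0.05 (two-sided assumed), 10% colonized. The two-proportion formula gives

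n = [1.96·√(2·0.62·0.38) + 0.842·√(0.85·0.15 + 0.39·0.61)]² / 0.46² ≈ 16.25.

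With the continuity correction,

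(16.25/4)·[1 + √(1 + 4/(16.25·0.46))]² ≈ 20.4, so 21 colonized patients per arm.

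Dividing by 0.10 gives 210 per group and 420 in total, as stated. The other two rows (160 and 240) also reproduce, so there is no arithmetic error here.

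**3. Power is not the main harm.** Section VII expects 50-55 randomized, about 25 per arm at the lower figure. At 85% versus 39%, with loss rates that are assumptions:

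| Loss | Evaluable per arm | Power, normal approximation | Power, exact Fisher | Randomized needed for 50 evaluable |
|---|---|---|---|---|
| 0% | 25 | 94% | 91% | 50 |
| 10% | 22 | 91% | 84% | 50/0.9 → 56 |
| 20% | 20 | 88% | 82% | 50/0.8 → 63 |
| 30% | 18 | 84% | 77% | 50/0.7 → 72 |

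At the plan's own drop-out rate (50/550 = 9.1%), 55 must be randomized, the top of the expected range.

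**4. Illustration of the bias.** Assume 25 active patients, of whom k are removed before the 6-month swab; 39% colonized among those who remain; 85% (the plan's untreated rate) among those removed; and no removals from placebo. Then

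as-randomized active rate = [(25 − k)·0.39 + k·0.85] / 25.

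| k | As-randomized | Observed | Overstatement |
|---|---|---|---|
| 2 | 10.67/25 = 42.7% | 39% | 3.7 points |
| 3 | 11.13/25 = 44.5% | 39% | 5.5 points |
| 4 | 11.59/25 = 46.4% | 39% | 7.4 points |
| 5 | 12.05/25 = 48.2% | 39% | 9.2 points |

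Taking 39% instead as the true as-randomized rate and solving for what would be observed, (0.39 − 0.85·d)/(1 − d), gives 33.9% at d = 10% and 27.5% at d = 20%. The direction is the same; the size depends on the starting point.

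**5. Range with no assumption about who is lost.** With completers at 85% and 39% and a fraction d lost in each arm, worst- and best-case imputation put the 46-point difference between 0.46·(1 − d) − d and 0.46·(1 − d) + d:

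- d = 10%: 31 to 51 points
- d = 20%: 17 to 57 points
- d = 30%: 2 to 62 points

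**The case against.** The strongest reply is that item b does not name non-use of product. Adherence is recorded by questionnaire (5.1 and 6.3), with no consequence attached. Section 6.3 places that questionnaire at the next scheduled visit. For a non-local patient this is the 6-month visit itself, when the outcome swab is also taken. Treatment is a single 7-day course, so over two years failing to comply more naturally means missed visits or swabs, and some such patients would have no 6-month swab under any rule. This stands. A reader might infer that the plan removes non-users and so compares compliers only; the documents do not say so. They leave item b open, and for a local patient non-use could come to light at the first 28-day visit.

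Two further replies also stand. No bias mechanism is evident for items e and f, which mirror the entry exclusions in 5.4. Item f covers only new healthcare work with direct patient contact, not any change of employment. For a woman positive at the pre-dispensing test, the order of test and randomization is not stated, so not every pregnancy termination is clearly a loss after randomization.

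The drop-out allowance and the minimum of 50 subjects with 6-month data protect numbers, not balance between the arms. Section 5.2 expects about 38 per arm, which would give more slack than section VII does. Neither removes the inconsistency within 6.10.

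**Conclusion.** The point holds in a limited form. Followed as written, 6.10 can discard outcomes after randomization for reasons that do not require it, and section VII has nothing to absorb the loss. The swab is lost only when termination falls between a randomization and the next 6-month visit. Item b carries the risk of bias; items e and f carry avoidable loss.

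The 4 to 9 points are an illustration, not an estimate. They rest on 25 per arm, on 39% applying to those who remain, on 85% among those removed, on removals from the active arm only, and on an assumed count, since the documents give no termination frequency. Section VII does not present 39% as a rate among compliers. Even the largest case leaves 48% against 85%, a 37-point difference, so it would be wrong to infer that the planned effect would vanish or that the trial is underpowered for this reason alone. The change is worth making because it is cheap and the protocol already contains the model for it.

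**What to change.** 1. In 6.10, separate no further study product or randomization from end of follow-up.
2. For randomized patients under item b, and under items e and f where the patient agrees, continue the scheduled swabs and questionnaires as already provided after a drug reaction. A patient who withdraws voluntarily still leaves under item a.
3. State that the five swabs are taken at the required termination visit, and add that visit to Appendix D. Reconcile the Appendix D unscheduled-visit column with the assessment list in 6.3.
4. Reconcile the statements on termination for pregnancy in 6.3, 6.4, 6.7, 18.C.6 and the Appendix D footnote with the new wording. Amending 6.10 alone would create contradictions.
5. In section VII, state that available outcomes are analysed by randomized arm, and how a 6-month swab that is still missing is treated.

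The cost is amendment wording and a few extra swab sets at visits that already exist. Nothing here changes who may receive study product, and no view is taken on that.

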- (2) Is the treatment effect different for repeat administrations of hexachlorophene/mupirocin? The rate of MRSA positive versus negative for recolonization reoccurrence through the sequence 1 versus 2 versus 3 versus 4 treatments will be assessed by a test of trend.
- (3) Is there a persistent or repeated-treatment effect? The overall rates of MRSA recolonization at 6, 12, 18, and 24 months will be assessed by a test of trend.
- (4) Is there an individual propensity for susceptibility and what are the treatment differences between placebo and hexachlorophene/mupirocin in terms of length of time for being negative for MRSA colonization on repeated testing? A Kaplan-Meier long-rank test will be conducted on three groups: initially negative, initially positive treated with hexachlorophene/mupirocin, and initially positive treated with placebo, where survival is defined as not having acquired MRSA.

For the secondary objectives, part (a) will be assessments of the rates in which prevalence is defined as the number of patients colonized with MRSA at the beginning of

the study divided by the total population studied, and the incidence as the number of new infections per calendar time divided by the total population studied. For objective (b) examining for predictors of MRSA, we will create a multivariate logistic regression model and use a backward stepwise approach. For part (c), to evaluate if there is a significant change in the CD4 count and/or viral load pre- versus during a MRSA infection we will utilize a 1-way ANOVA. We will also compare pre-MRSA infection with after MRSA resolution as well as the counts during the infection with those after resolution. Finally, objective (d) will be a descriptive analysis of the molecular and microbiologic characteristics of the isolates. The main statistical data from the retrospective chart review study of HIV patients at NMCSD will be presented by descriptive analyses. We will compare demographics and HIV clinical data between those with and without MRSA using rank sum tests and Fisher's exact tests depending on the variable characteristics (categorical or continuous). A multivariate logistic regression model for predictors of MRSA will then be developed using a backward stepwise approach using Stata software.

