Hence to show a statistically significant decline in colonization rates using mupirocin (Bactroban®) and hexachlorophene (pHisoHex®), up to 420 patients would be required. Given potential lost to follow-up events and that the colonization rate or clearance rates may vary, we propose to enroll 550 participants, such that 500 participants are followed throughout the study period. Given this sample size and the estimate of a 10% colonization rate over the study period, we would estimate that 50-55 participants will be randomized. Since participants with repeat colonization events may differ from those with first time MRSA colonization and may differ in response to decolonization medications, we will also examine as a secondary analysis of the primary endpoint only those with unique randomizations.

For showing a significant difference in the number of infections between the two treatment groups, assuming 38% of the no specific treatment group and 10% of the treatment group will develop infection, a sample size of 860 would be needed; of note, this is a secondary objective and not the primary basis of the sample size calculation for this study. For smaller changes in the difference in the rates between groups, larger sample size would be needed. Of note, the first rates (38% vs. 10%) were determined during an 8-10 week period and our study involves 6-month periods over a total two year period; on the other hand, this military training population studied for these estimates may have a higher rate than our HIV patients.

Infection Rate in Treated Group	Infection Rate in Placebo Group	Difference in Infection Rate Between Groups	Power	Alpha level	Total sample size for one time period	Total sample size for every 6 month evaluations
10%	38%	28%	.80	.05	860	277
10%	30%	20%	.80	.05	1440	464
10%	25%	15%	.80	.05	2260	729
5%	15%	10%	.80	.05	3200	1032

To account for the study design of patients being re-examined every 6 months over a two-year period (a total of five visits) and re-randomized at each of these intervals with new infections being counted as separate events, the sample size required was notably smaller (last column in table). The calculations accounted for a progressive decrease in colonization and infection rates over the course of the study since patients would be given decolonization medications depending on their randomization assignment.

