Using these data, we proposed a sample size of 500 participants to find statistically significant results; given the long duration of follow-up and the possibility for attrition, we will enroll 550 participants accounting for 50 drop-outs.

Overall, we plan to enroll 550 participants into the study with the goal of a minimum of 50 randomizations for scientific significance. In addition, we will also examine unique randomizations, defined as a subject's initial randomization (not counting re-randomizations), as a sub-analysis of the primary endpoint. Of note since the primary endpoint includes completion of the 6 month follow-up visit after initial randomization, at least 50 subjects with these data are needed.

We plan to conduct an interim examination yearly (after at least one-half of subjects are enrolled) to determine the adequacy of the design assumptions and sample size, given that there is little literature regarding the expected colonization and infection rate in this specific (HIV) population. Also, approximately every year we will conduct an examination of the epidemiologic data regarding the prevalence and incidence of MRSA in this cohort, as well as a safety assessment.

We also calculated a sample size for the secondary objective which was to determine the predictors of MRSA colonization and infection among HIV-infected persons including examination of demographics, sexual activity, hygienic procedures, drug use, antibiotic and HAART medications, sexually transmitted diseases and HIV control. Of note, the other secondary objectives do not lend themselves to sample size calculation due to the paucity of baseline data in the literature. Predictors for MRSA were examined in three studies including Mathews et al, Lee et al, and our retrospective work [7, 12, 13]. For a power at 80%, alpha of 0.05, and examining 20 potential predictors with an R^2 of 0.10, we would need to enroll 205 patients in the study (sample power analysis, SPSS). As we examined more predictors, a larger sample size (500 to 550) is preferred.

VIII. DATA ENTRY AND ANALYSES

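### Section VII calls four questions primary, two of them active-versus-placebo comparisons of colonization, and ranks none, so the stated .05 holds only if one test is named in advance

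*Combined protocol and SAP*

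**What the plan says.** Section VII opens with "There are four primary questions to be answered to address" the primary objective.

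- **Question (1)** asks for the treatment effect on clearing colonization: "We propose to pool the data at 6, 12, 18, and 24 months as if they were independent and conduct a chi-square or Fisher's". The second option named is Fisher's exact test, and no rule chooses between the two. The text admits that pooling assumes no persistent or repeated-treatment effect and no difference in susceptibility between patients, and says the later questions will look into this.
- **Questions (2) and (3)** are tests of trend, over the number of treatments and over visits.
- **Question (4)** asks about individual susceptibility and also about "treatment differences between placebo and hexachlorophene/mupirocin in terms of length of time for being negative for MRSA colonization on repeated testing". Its log-rank test is run "on three groups: initially negative, initially positive treated with hexachlorophene/mupirocin, and initially positive treated with placebo".

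The sample size text in the same section says of repeat carriers that "we will also examine as a secondary analysis of the primary endpoint only those with unique randomizations". Section 3.1 and a later paragraph of Section VII call the same analysis a sub-analysis. The sentence after that later label reads differently: "since the primary endpoint includes completion of the 6 month follow-up visit after initial randomization". From this it concludes that no fewer than 50 subjects must have such data. Section 6.3 restates the primary endpoint with no time point, unit of analysis or test.

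Alpha of .05 appears only in the sample size text and tables. Nothing orders the tests or adjusts for their number.

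**The concern.** Two analyses that carry the primary label answer the same question, active versus placebo on colonization, with different units and different tests. One clause points to a third. If they disagree, the plan does not say which one is the trial's answer, so the choice could be made after the results are known. A level of .05 for one test does not then describe the chance of a false claim.

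The choice also affects what the result means. The pooled test counts a persistent carrier again at each re-randomization and needs the assumptions that Section VII concedes. A first-randomization test needs neither assumption.

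**Working it through.** **1. What the stated .05 covers.** Inputs from Section VII: 85% of the untreated and 7%, 23% or 39% of the treated remain colonized; power .80; alpha .05; 10% of patients colonized; 1:1 allocation. With d the difference in proportions and p̄ their mean:

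n′ = [1.960·√(2p̄(1−p̄)) + 0.842·√(p₁(1−p₁) + p₂(1−p₂))]² / d²

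n = (n′/4)·[1 + √(1 + 4/(n′d))]² (continuity-corrected)

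For 85% v 39%: n′ = (1.345 + 0.509)² / 0.46² = 16.25, and n = (16.25/4)·(1 + √1.535)² = 20.4, so 21.

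| Treated rate | n per arm | Carriers per arm | ÷ 10% | Plan, per group (total) |
|---|---|---|---|---|
| 7% | 7.4 | 8 | 80 | 80 (160) |
| 23% | 11.9 | 12 | 120 | 120 (240) |
| 39% | 20.4 | 21 | 210 | 210 (420) |

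The table reproduces exactly. Without the correction the result is 60/90/170 per group; one-sided with the correction it is 70/100/170. So .05 is the level of one two-sided two-proportion test with one record per carrier.

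**2. Competing versions of the colonization comparison.**

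| Version | Unit | Test | Label in the plan |
|---|---|---|---|
| Question (1) | every randomization, pooled | chi-square or Fisher's exact | primary |
| Question (4), second half | patient, time negative | three-group log-rank | primary |
| 6-month visit after first randomization | patient | none named | primary endpoint in one clause; secondary or sub-analysis in three places |

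**3. Weight of repeat randomizations in the pool.** Take 55 first randomizations and an average persistence q = (0.85 + p)/2 = 0.46, 0.54 or 0.62. Ignore attrition and recolonization after clearance.

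- All first randomizations at baseline: records = 55·(1 + q + q² + q³) = 97, 109, 123. Repeats = 1 − 55/records = 43% to 55%.
- First randomizations spread evenly over months 0, 6, 12 and 18 (assumption): average the sums of 4, 3, 2 and 1 terms. Records = 55 × 1.475 to 55 × 1.717 = 81 to 94. Repeats = 32% to 42%.

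**4. Error rate if any significant version may be reported.** Null simulation, 3,000 trials in each of 12 scenarios. These inputs are assumptions:

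- 50 or 76 carriers (76 is the 38 per arm in Section 5.2);
- first randomization spread evenly over months 0-18;
- (staying positive, recolonizing) per 6 months of (85%, 10%), (50%, 10%) or (50%, 30%);
- no between-patient variation, or variation with SD 1.5 on the logit scale;
- six-monthly visits only, and a two-arm log-rank test.

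| Test at .05 | Rejection rate, range over scenarios |
|---|---|
| Pooled chi-square alone | 4.5-5.9% |
| First-randomization chi-square alone | 4.0-6.3% |
| Two-arm log-rank alone | 4.4-5.6% |
| Pooled or log-rank | 7.8-9.3% |
| Any of the three | 8.6-11.1% |

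The Monte Carlo standard error is about 0.4-0.6 points. A separate run with 54 carriers, mean persistence about 0.6 and variation between patients gave 9.5% for any of three with chi-square and 8.0% with Fisher's exact test.

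**5. Cost of the alternatives in the hardest case (85% v 39%).** One named test: 2 × 21 = 42 carriers. Bonferroni over two, three or four tests: 24, 27 or 28 per arm, so 48, 54 or 56 carriers. Section VII expects 50-55 randomized participants.

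**The case against.** The best counter-reading is that a hierarchy is implied. Question (1) states the treatment effect, lists its assumptions and hands them to the later questions. That reading fits (2), (3) and the first half of (4). It does not fit the second half of (4), which asks for a treatment difference outright. Nor does the plan say which result stands if the assumptions fail.

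Several stronger readings are tempting, and the documents do not support them.

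- **That four primary tests give an 18.5% error rate** (1 − 0.95⁴). Questions (2) and (3) are not active-versus-placebo tests, and all the tests share patients. This figure should not be quoted.
- **That there are three equal definitions of the primary analysis.** The third rests on one clause, which may only count evaluable subjects. The two labelled analyses are enough for the point.
- **That the sample size table shows the first-randomization analysis was the intended primary.** It could equally be a conservative sizing of question (1) that takes no credit for repeats.
- **That the pooled test is itself the source of the inflation.** Taken alone it held about 5% in simulation. The fault is the missing designation.

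It also stands that the simulated log-rank has two arms and the planned one has three. A significant three-group result could come from the initially negative patients alone, so the planned test would not by itself establish a treatment difference.

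**Conclusion.** The point holds. Section VII labels two different active-versus-placebo tests of colonization primary, adds a clause pointing to a third, and gives no ranking or alpha rule. The .05 fits one comparison.

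If any significant version may be the headline, the false-positive rate is about 8-9% for the two analyses labelled primary and about 8-11% for all three. These figures depend on assumed persistence and recolonization and on a two-arm log-rank contrast. The plan does not say that it will report whichever test succeeds; it fails to rule that out. Repeat randomizations would make up about 32-42% of pooled records if first randomizations are spread over months 0-18, or 43-55% if all occur at baseline, so the versions could plausibly differ.

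**What to change.** Name one primary test in Section VII. The preferred choice is 6-month MRSA status after each patient's first randomization, by assigned arm, at two-sided .05, with chi-square or Fisher's exact test fixed in advance. It matches the unit of the sample size table and does not need the pooling assumptions. Naming question (1) alone would also remove the multiplicity, but would keep those assumptions.

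Label the remaining analyses supportive, and specify an active-versus-placebo contrast within question (4). Bring Sections 3.1, 6.3 and VII into line. That includes the rule in Section 6.3 that takes participants decolonized at the clinician's wish out of the placebo group for analysis, since it conflicts with analysis by assigned arm. The clinician's freedom to treat is not in question here.

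The cost is a formal protocol amendment under Section 18.C.10, because the objective and endpoint text change. No extra patients are needed: 42 carriers in the hardest case, against 50-55 expected. The downside is that repeat randomizations become supportive evidence only.
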